7.2.3 End of therapy

The information in this document is the property of OncoEthix and is confidential. Neither the document nor the information contained therein may be reproduced or disclosed outside OncoEthix without their written consent

.

8. Other Investigations As clinically or biologically indicated.

7.2.4 Follow-up

After the end of therapy visit, subjects will be followed until resolution of TEAEs possibly related to the study treatment or the return to baseline value, if abnormal, or the categorization into sequella.

All deaths occurring within 30 days after the last dose of study treatment (regardless of relationship to study treatment), or considered related to study drug treatment (regardless of their date of occurrence) will be reported as serious adverse events (SAEs). Deaths occurring more than 30 days after the last study medication administration and not related to drug treatment will not be considered as SAEs.

7.3 METHODS

7.3.1 Efficacy data

7.3.1.1 Tumor assessment methods

• Patients with evaluable tumor masses (e.g. lymphomas)

To ensure comparability, the baseline and subsequent tumor measurements to assess response should be performed using identical imaging techniques (i.e., CT-scan or MRI, or PET-scan, preferably the same machine, identical contrast agent and standard volume of contrast agent...).

Superficial skin lesions or visible adenomegaly will be photographed.

• Bone marrow biopsy

Bone marrow biopsy will performed each time it is necessary to assess appropriately tumor response (e.g. lymphoma or other disease if bone marrow aspiration is technically impossible). Bone marrow biopsy at day 43 may be omitted if normal at baseline.

• Bone marrow aspiration

Will be used to assess response in acute leukemia and multiple myeloma

• Plasma M-component (protein electrophoresis) and/or Bence-Jones proteinuria

Will be used to assess response in multiple myeloma.

7.3.1.2 Tumor assessment criteria

The lesions will be assessed throughout the study according to standard criteria, for lymphomas [*Cheson 2007*], and multiple myeloma [*Durie 2006*]. Patients with acute leukemia will be assessed based on the recommendations from the European LeukemiaNet [*Döhner 2010*] For details, see section 16.10; Appendix X.

Nonetheless, in the context of a phase I study, any tumor shrinkage will be quantified and recorded, even though it does not meet admitted criteria for response, as clue of clinical activity.

7.3.1.3 Overall survival (OS)

Survival is defined as the duration between the date of first OTX015/MK-8628 intake and the date of death whatever the cause, or censored at the date of last contact if there is no documentation of death before the cut-off date.

7.3.2 Safety data

All the tests and laboratory measurements that will be performed prior and/or on specific days during and following therapy are described in section 7.2.

7.3.2.1 Clinical Safety

Clinical and physical examinations, as well as vital signs evaluation, will be performed. Patient data will be analyzed for evidence of cumulative toxicity with repeated cycles of therapy.

TEAEs / signs and symptoms of disease observed by the investigator (preferably by the same physician for a same subject) or reported by the subjects to the study nurses will be recorded and graded according to NCI-CTCAE version 4.02, accessible via internet [http://evs.nci.nih.gov/ftp1/CTCAE/CTCAE_4.02_2009-09-15_QuickReference_8.5x11.pdf]. It is crucial that all events, even if not related to the study drug are reported in the CRF.

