	to be done within 7 days prior to first study drug administration (except tumor imaging, bone marrow biopsy and LVEF within 30 days and	D1	D8	D15	D22	q3 wks from day 22 onward	TREATMENT
	informed consent and blasts sampling within 14 days)	V1	V2	V3	V4	V5 and higher	ЕОТ
Informed consent	X						
History incl. baseline concomitant illnesses; , Height	X						
Pregnancy test	X						
Availability of archived biopsy for lymphoma	X						
Physical examination (ECOG Performance Status (PS), Weight, clinical tumor measurement)	X	X	X	x	X	x	X
Vital Signs	X	x ⁽¹⁾	x	x	X	x	X
12-lead ECG	X	x ⁽¹⁾			x	x	X
Baseline symptoms / Adverse events	X	X	x	x	X	x	X

Clinical Study Protocol OTX015_104	Date: 18 December 2015 Document Status: Version J						
Prior / concomitant medications	X	X	x	x	X	x	X
Peripheral blood Hematology (*)	X	X	X	x	x	x	X
Bone marrow aspiration (²)	X		(x)		(x)	(x)	
Biochemistry (**)	X	X	x	x	x	x	X
Imaging/Tumor assessment (***)	X					x ⁽³⁾	X
Plasma M-component and/or BJ proteinuria (myeloma only)	X				X	x	X
Fresh tumor cells sampling ⁽⁴⁾ for baseline predictive biomarkers, PD biomarkers and intracellular PK	X			x ⁽⁵⁾			
Bone marrow biopsy, (****)	X					x ⁽⁶⁾	
Urinalysis°	x	X	x	x	x		X
Blood Pharmacokinetic (PK) sampling		X ⁽⁷⁾	x ⁽⁸⁾	x ⁽⁸⁾	x ⁽⁸⁾		
Echocardiography with LVEF measurement	X						X

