11 STATISTICAL PROCEDURES

11.1 ANALYSIS VARIABLES/ STUDY ENDPOINTS

Primary: DLT is the endpoint for the determination of the RD in each subset.

Secondary: treatment-emergent adverse events (TEAEs), vital signs, laboratory results, ECG and LVEF changes, PK and PD parameters, disease specific tumor response assessment, quantitative tumor shrinkage, tumor-related symptoms, PS.

Exploratory: Predictive factors of clinical activity: clinical features / tumor phenotype/ cytogenetics / molecular biology markers / gene expression profile,

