#### **Study endpoints**

- Primary: the primary endpoint for the determination of the RD will be DLT
- Secondary: treatment-emergent adverse events (TEAEs), PK and PD parameters, laboratory results, tumor response assessment (according to most recently published standard criteria) (see details by disease in the core protocol), tumor-related symptoms, performance status (PS).
- Exploratory: tumor phenotype, karyotype, molecular biology, etc.

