# **10.1 DEMOGRAPHICS**

- Age (years; by category) and gender.
- ECOG performance status at the screening visit by score (0, 1, 2, 3, 4)
- Height (cm), weight (kg), BMI (kg/m^2) = weight in kg/(height in m) and BSA (m^2) = (W 0.425 x H 0.725) x 0.007184.
- Pregnancy test (positive, negative, NA)

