# **12.4 ADVERSE EVENTS**

Adverse events occurring or worsening after the treatment start date and before the last study treatment administration date +30 days were considered treatment-emergent adverse events (TEAEs).

- 21 -

Summary AEs (number and % of patients) will be tabulated by DL and overall for patients with:

- at least one treatment-emergent grade 1-5 adverse event (TEAE)
- at least one related treatment-emergent grade 1-5 adverse event (TEAE)
- at least one treatment-emergent grade 3-5 adverse event (TEAE)
- at least one related treatment-emergent grade 3-5 adverse event (TEAE)
- at least one serious TEAE
- at least one serious TEAE related to the study treatment
- a TEAE leading to treatment discontinuation
- a related TEAE leading to treatment discontinuation
- a TEAE leading to death

Tables of individual TEAEs (number and % of patients) grouped by primary System Organ Class (SOC) and Preferred Term (PT; for MedDRA) will be presented by DL and overall. Patients will be counted only once per primary SOC and PT.

These tables will be presented for all cycles as well as for cycle 1 only.

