## AE TABLES FOR ALL CYCLES AND CYCLE 1 ONLY

Table iii-2 NCI-CTCAE grade 1-4 AEs regardless of relationship to treatment, worst grade per patient, AL / OHM/ ALL PATIENTS safety population

Adverse event	
N patients with ≥1 AE / N AE	
SOC	
РТ	
PT	

Data source: Statistical Output, Section

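### The promised analysis of cumulative toxicity and two secondary endpoints (on-study PS and tumour-related symptoms) have no summary in the SAP and are not declared as changes from the protocol

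*Protocol*

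**What the plan says.** **Cumulative toxicity.** Protocol 7.3.2.1 commits to an analysis without giving a method: "Patient data will be analyzed for evidence of cumulative toxicity with repeated cycles of therapy". On the adverse-event tables, SAP 12.4 says: "These tables will be presented for all cycles as well as for cycle 1 only". The appendix shells carry the same split under the heading "AE TABLES FOR ALL CYCLES AND CYCLE 1 ONLY". SAP 12.2 and Table ii-2 count reductions, interruptions and delays per patient, not per cycle.

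**PS and tumour-related symptoms.** The secondary endpoints in Protocol 11.1 end with "quantitative tumor shrinkage, tumor-related symptoms, PS", and the SAP synopsis keeps the last two of these. The protocol flow chart collects PS with the physical examination at baseline, days 1, 8, 15 and 22, every three weeks after that, and at end of treatment. SAP 10.1 summarises PS at the screening visit, and the Table iii-1 shell shows it among baseline characteristics. SAP 10.3 tabulates signs and symptoms present at baseline and as medical history.

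**Declared changes.** SAP 14 lists three: no per-protocol analysis, no overall survival analysis, and no PK/safety, PD/safety or PK/PD analyses.

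**The concern.** The recommended dose (RD) rests on DLTs in the first 21 days, apart from the haematological DLT in acute leukaemia, which is confirmed at day 43 (Protocol 3.2). Treatment then continues until progression or intolerable toxicity (Protocol 5.3). The expansion part is meant to confirm feasibility and safety at the RD, and it opens only once at least 3 patients per subset have received at least 2 cycles (Protocol 3.1.2). The protocol thus treats tolerance after cycle 1 as relevant, and its cumulative-toxicity sentence is the commitment to look at it.

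A crude count over all cycles rises with time on treatment even if the risk per cycle never changes. If that is the only AE summary reaching past cycle 1, a reader cannot tell accumulating toxicity from long exposure. For PS and symptoms, the SAP's own endpoint list leads a reader to expect results, and there would be neither a table nor a reason for its absence.

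**Working it through.** The plan states no figure on this point, so the main check is a comparison of texts.

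| Protocol item | Planned SAP summary | Listed in SAP 14? |
|---|---|---|
| Cumulative toxicity over cycles (7.3.2.1) | AE tables for all cycles and for cycle 1 (12.4 and shells) | No |
| PS on study (11.1) | Screening or baseline only (10.1, Table iii-1) | No |
| Tumour-related symptoms on study (11.1) | Baseline and medical history only (10.3) | No |

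All three items lack a dedicated summary, and none of the three is declared. SAP 11 does not fill the gap. Its response tables, waterfall plots and list of signs of activity for narratives include neither PS nor symptoms.

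**Does another output supply the missing AE analysis?**
- Table ii-1 tabulates cycles started (rows 1, 2 and 3 in the shell), but apart from the events.
- SAP 12.6.1 and 12.7.1 describe laboratory values and vital signs by visit. They do not measure symptomatic AEs by cycle.
- Table vi-3 gives time to first grade 3 and grade 4 thrombocytopenia and its duration, for one toxicity in the OHM (other haematological malignancies) subset.
- SAP 12.4.1, 12.7.3 and 15 provide listings, which are raw data.

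**Can the two AE periods be contrasted?** Assume, for illustration, a constant risk p = 0.10 per cycle and no accumulation. Incidence over k cycles is 1 − (1 − p)^k.
- k = 2: 1 − 0.9² = 0.19
- k = 6: 1 − 0.9⁶ = 0.469
- Ratio: 0.469 / 0.19 ≈ 2.5
- All-cycle minus cycle 1: 0.19 − 0.10 = 0.09 for two cycles, and 0.469 − 0.10 = 0.369 for six

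The difference is positive and grows with duration although the risk is flat. A patient count after cycle 1 therefore needs the number at risk in each later cycle before it says anything about accumulation.

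**Which denominator?** Under the same assumption, with everyone staying on treatment, first events divided by all starters are 0.10, 0.10 × 0.9 = 0.09 and 0.10 × 0.9² = 0.081 in cycles 1, 2 and 3. That is a false decline. Divided by starters who are still event-free, the rate is 0.10 each time.

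**Is there enough data?** From the column headers in SAP 6.1:
- AL, 80 mg QD 14-21: 19 + 16 = 35 expansion patients, plus 4 escalation patients on the same regimen (DL4A) = 39.
- OHM, 80 mg QD 14-21: 16 expansion patients. The 7 escalation patients at 80 mg QD were on 21-21, a different schedule.
- The other escalation columns have 3 to 8 patients each.

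These are numbers at entry. The documents do not say how many reached later cycles.

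**The case against.** The strongest case against is that the SAP is far from silent on safety over time. For each preferred term, all-cycle patients minus cycle 1 patients gives those whose first event came later. Cycles started are tabulated by dose level. Laboratory values and vital signs are shown by visit. Thrombocytopenia timing is summarised for OHM, and every AE is listed with dates and grade. The protocol prescribes no method and does not name cumulative toxicity among its objectives or endpoints. New or worsening disease symptoms are recorded with TEAEs (SAP 12.1), and on-study PS may appear in the physical examination listing. Escalation groups of 3 to 8 patients split by cycle would give almost empty cells.

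Much of this stands, and it rules out several stronger readings that a reader might infer:
- *That the trial cannot address late toxicity, or that the SAP gives no number at risk.* The data are collected, and cycles started are reported. What is missing is an AE summary that joins the two.
- *That longer-treated dose levels will look more toxic.* The cycle 1 tables compare dose levels over one common window, SAP 6.1 gives percentages only in the overall column, and no tests are planned.
- *That the bias is 2.5-fold.* The 10% risk and the two and six cycles are assumptions. The documents report no treatment durations by dose level.
- *That by-cycle tables are needed at every dose level.* They would be too sparse.

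What does not stand is that these outputs amount to the promised analysis. The subtraction fails without later-cycle denominators, as shown above, and a listing is not an analysis. Counting worsening symptoms as TEAEs leaves improvement in symptoms or PS without any summary.

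**Conclusion.** The point holds as a gap between commitment and plan, not as a flaw in the trial's main result. Three protocol items have no dedicated SAP summary and no entry in SAP 14. The planned AE summaries cannot separate accumulation from longer time on treatment; the other safety outputs give only a partial view.

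The size is modest. The study is descriptive, PS and symptoms are secondary endpoints, and the DLT analysis and the determination of the RD do not depend on these tables. A reader might infer that the RD itself is in doubt. The documents do not support that: Protocol 11.1 bases it on DLT, and Protocol 11.3 defers validation to phase II studies. The 19% and 47% figures show a mechanism under an assumed constant risk and estimate nothing about this trial.

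The conclusion assumes that the SAP sections and shells show all planned summaries apart from the PK and PD evaluations, which are reported separately.

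**What to change.** 1. Add one descriptive table per subset (AL, OHM) for the 80 mg QD 14-21 regimen, using the expansion cohorts plus any escalation patients on that same regimen. For cycles 1, 2, 3 and ≥4, give the number of patients with a grade ≥3 TEAE, with a related TEAE, and with a dose reduction or interruption in that cycle, over the patients starting that cycle. If first events are counted instead, divide by patients starting the cycle still event-free. For other dose levels a listing is enough.
2. Add a shift table of best and worst on-study ECOG PS against baseline.
3. Tabulate on-study change in tumour-related symptoms, or state in SAP 14 that it was dropped and why.

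The cost is two or three extra descriptive tables from data already collected, with no tests. SAP 16.1 already allows the outputs to change during programming by agreement between the sponsor's representative and the statistician. The limit is small later-cycle denominators. Patients who reach those cycles are also a selected group, some on reduced doses, so the table should be read as description only.

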7.3.2.2 Laboratory measurements

All clinically significant laboratory values require to be reported as TEAEs in the CRF. Clinically significant laboratory results are those, which have clinical consequences (i.e. need for treatment or corrective measures, study drug dose reduction or interruption or discontinuation, hospitalization, prolongation of hospitalization, death, or are life-threatening, or are reported as SAE whatever the reason). The seriousness, the action taken regarding study medication and patient participation in the study, relation to study medication and the most likely cause, should then be recorded.

Other laboratory changes, even severe in intensity (i.e. NCI-CTCAE grade 3-4), but without the aforementioned clinical consequences, are not clinically significant. They will be only reported in the laboratory results part of the CRF and should not be reported in the TEAE part of the CRF.

The information in this document is the property of OncoEthix and is confidential. Neither the document nor the information contained therein may be reproduced or disclosed outside OncoEthix without their written consent

7.3.3 Pharmacokinetics (PK)

7.3.3.1 PK sampling schedule

7.3.3.1.1 Blood collection schedule

1. Once-a-day schedule

- At each dose level (DL) 3 patients will have complete PK sampling. Other patients will have limited PK sampling. All patients enrolled at the same DL across both subsets (AL/other hematological malignancies) will be considered for the selection of the 3 patients with complete PK sampling. Patients hospitalized due to medical reasons will be first considered for complete PK sampling.
- Patients with complete PK sampling:

Seven blood samples will be collected for PK analysis on days 1-2: T0,(before dosing), then T1h, T4h, T8h, T12h, T24h + either T10h or T16h (one of these points mandatory) (Table 4).

• Patients with limited PK sampling

Five blood samples will be collected on day 1: T0,(before dosing), then T1h, T4h, T6h, T8h.

- 2. Twice-a-day (BID) schedule
- All patients will have complete PK sampling during a 24-hour inpatient hospitalization. Height blood samples will be collected on days 1-2: T0 (before dosing), then T20min±5min, T1h±10min, T2h15min±15min, T3h15min±15min, T9h±1h, T12h±15min (just before the second intake), T24h (before drug dosing)

In all patients residual plasma concentration (C_{min}) will be assessed just before drug intake, at days 8, 15 and 22

- Three mL of blood will be collected in a peripheral vein for each sample, corresponding to a total of 21 mL of blood drawn on day 1-2 for patients with complete PK sampling and 15 mL of blood drawn on day 1 for patients with limited PK sampling. In addition, a total of 9 mL of blood will be collected on days 8, 15 and 22. In total, 30 mL of blood will collected for PK for patients with complete PK sampling and 24 mL for patients with limited PK sampling.
- Collected blood samples will be centrifuged immediately. Late samples (T10-16h) can be left vertically into refrigerator and centrifuged early in the morning the day after. Plasma will be harvested, then stored at -20°C until centralized collection. See Appendix IV, section 16.4 for sample centrifugation, storage and shipment

		Sa	mpling Tim	ne for OTX0	15/MK-862	8 concentra	tion			
	T0 (just before OTX015/MK- 8628 administration)	T1h		T4h	T6h	T8h	T10h	T12h	T16h	T24h
	PATIENTS WITH COMPLETE PK SAMPLING (once-a-day)									
Day 1-2	x	x		x	-	x	X*	x	X*	X (just before OTX015/ MK-8628 administr ation)
	PATIENTS WITH LIMITED PK SAMPLING (once-a-day)									
Day 1	X	Х		Х	Х	Х	-	-	-	-

Table 4: Blood sampling schedules for OTX015/MK-8628 pharmacokinetics

	PATIENTS WITH COMPLETE PK SAMPLING (twice-a-day)											
OTX015/MK- T20min T1h T2h15 T3h15 T9h OTX015/MK-8628 OTX015/MK-							T24h (just before OTX015/MK- 8628administration)					
Day 1-2	X	Х	Х	Х	Х	Х	Х	Х				

ALL PATIENTS										
Day 8, 15, 22	Х	-		-	-	-	-	-	-	-
·										

*only one of these (10h or 16h)

7.3.3.1.2 Fresh tumor cells

Concentration of OTX015/MK-8628 will be measured in tumor cells.

- Fresh leukemic cells will be collected either from peripheral blood or bone marrow (depending on the number of blasts available) on day 8.
- For patients with other malignancies, optional fresh tumor biopsy will be obtained after specific consent at baseline (between day -14 and day 1) and at day 15 ± 7 from superficial lymph nodes, or any other easily accessible tumor without invasive procedure. See Appendix IV, section 16.4 for sample centrifugation, storage and shipment

Of note, fresh cells collected on day 8 (AL) or 15 ± 7 (other hematological malignancies) will be also used for assessment of pharmacodynamic biomarkers (see section 7.3.3.1.2). The total blood or marrow volume for PKwill be 7 and 3 mL respectively.

7.3.3.2 Assay method:

Plasma and tumor concentrations of OTX015/MK-8628 will be measured using Ultra Performance Liquid Chromatography with tandem Mass Spectrometry detection (UPLC-MS/MS).

The following parameters will be determined: Trough (Cmin) and peak (Cmax) concentrations, Tmax, AUC $[0-\infty]$, Vdss, t1/2, steady state, total Clearance (CL).

7.2.4.7 Pharmacokinetic analysis:

Pharmacokinetic analysis will be carried out using the nonlinear mixed effect modelling software program Monolix version 412. (http://wfn.software.monolix.org).

7.3.4 Pharmacodynamic assessment

PD biomarkers in tumor cells will be explored in tumor cells. Based on current knowledge, c-MYC and BRD2, 3 and 4 expression will be measured. Other biomarkers could be explored according to increasing scientific knowledge.

7.3.4.1 Fresh tumor cells

Fresh leukemic cells will be collected from peripheral blood and bone marrow at baseline (between day -7 and day 1) and on day 8. *The total blood and marrow volume for PD will be 15 and 3 mL, respectively, each day.*

For patients with other malignancies, fresh tumor cells may be optionally obtained in selected patients at baseline (between day -14 and day +1) and at day 15 ± 7 days from superficial lymph nodes core biopsy, or any other easily accessible tumor without invasive procedure.

Of note, fresh cells collected on day 8-22 will be also used for assessment of intracellular PK (see section 7.3.3.1.2) and that collected at baseline will be assessed for predictive biomarkers (see section 7.3.6.1).

See Appendix V, section 16.5 for sampling technique, storage and shipment.

7.3.5 Pharmacokinetic / pharmacodynamic relationship

*PK/safety correlations*: The incidence and severity of AEs will be compared to Cmax, CL and AUC of OTX015/MK-8628.

PD/safety correlations: The incidence and severity of AEs will be compared to the most pertinent biomarkers, if any.

*PK/PD correlations*: Cmax, CL and AUC of OTX015/MK-8628 will be compared to the most pertinent biomarkers, if any.

7.3.6 Tumor phenotype/Predictive factors of clinical activity

7.3.6.1 Archived tumor material

Available archived tumor material will be collected. The availability of a paraffin-embedded block is a pre-requisite for inclusion of patients with lymphoma into the study if no fresh tumor tissue is available.

At least one H&E colored slide and 6 to 7 blank slides will be requested from the most recent biopsy.

Albeit not mandatory, archived bone marrow biopsy, if available, will also be requested in patients with multiple myeloma for analysis of predictive biomarkers.

7.3.6.2 Fresh tumor cells

Fresh leukemic cells will be collected from peripheral blood and bone marrow at baseline (day -14 to day +1).

For patients with other malignancies, mainly lymphoma, fresh tumor cells may be obtained in selected patients (optional and under specific consent) at screening from superficial lymph nodes core biopsy, or any other easily accessible tumor without invasive procedure.

Of note, fresh cells collected at baseline will be also used for assessment of PD biomarkers (see section 7.3.4.1).

